To address the secondary objective, participants will also be asked to provide pre- and post-travel biologic (stool) samples for laboratory testing for the presence of gut AMR genes (see Laboratory instruments). Timing of the pre- and post-travel data and stool sample collections will be within 7 days before departure and 10 days after return from travel, respectively. Both biologic (stool) samples will be self-collected and submitted by mail to the clinic (the collection kit, and all necessary packaging and postage will be provided to the traveler). The participant will not be seen by a healthcare provider involved with the study post-travel unless they are ill and seek an evaluation.

As part of standard pre-travel consultation practices, if indicated, travelers will be prescribed anti-diarrheal medications and/or antibiotics for self-treatment of TD. These medications may include loperamide (Imodium), diphenoxylate and atropine (Lomotil), BSS (Pepto bismol), ciprofloxacin, azithromycin, or rifaximin. If these medications are taken while abroad, the travelers will be asked to note this on the during travel or post-travel questionnaires.

No difference in pre-travel advice, provision of anti-diarrheal medications, or during- or after-travel medical evaluation or advice will occur based on the traveler's assigned study arm.

Duration of Subject Involvement

The duration of each participant's involvement in the study is expected to be a maximum of 6 weeks. This will account for time to complete the pre-travel consultation/enrollment visit, 21 days (or less) of travel, and post-travel follow-up.

How the Study Design Addresses the Objectives and Hypotheses

A double-blinded, placebo-controlled randomized clinical trial is the best study design to address the study objectives and hypotheses. We aim to determine if there is a biologic benefit to an intervention (BSS administration), and a placebo-controlled methodology is required to determine if there is a statistically significant benefit of the intervention

regarding incidence of TD and acquisition of gut AMR genes. It is imperative to blind both healthcare providers and participants to ensure that biases, including selection and observer bias, are minimized.

Stakeholder Participation

The primary stakeholders for the project are international travelers, healthcare providers, and public health officials.

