Based upon published reports, we anticipate that participants in the intervention arm of the study will experience a health benefit; they will be less likely to acquire TD while abroad. They also may benefit, in the event that they do acquire TD, by having a shorter duration and lesser severity of TD symptoms in comparison to those in the placebo group.

Description of the Potential Risks to Anticipated Benefit Ratio

The potential benefits of participating in this study outweigh the minimal risks.

Emergency Care

We do not anticipate participants needing emergency care as a part of this study.

Participants will be provided phone and email contact information for study personnel in the event questions or concerns arise that may relate to their participation in the study.

Study Timeline

Table 1. Study Timeline, 2017–2020

Study Component	Date of Anticipated Start	Date of Anticipated End
Protocol Writing and Coordination	March 2017	October 2017
Submission of protocol/consent forms for IRB approval	November 2017	Late December 2017
Training of study personnel	January 2018	January 2018
Enrollment of participants	February 2018	July 2019
Laboratory analysis of stool specimens	February 2018	October 2019
Data entry	February 2018	October 2019
Data analysis (every 3 months)	April 2018	November 2019
Manuscript writing and clearance	November 2019	March 2020
Dissemination of findings	March 2020	

Study Population

Description and Source of the Study Population

Participants will be selected from persons seeking a pre-travel consultation at The New York Center for Travel and Tropical Medicine, New York, United States. This clinic serves travelers by providing pre-travel consultative services, in addition to post-travel screening, assessment, diagnostic, and treatment services. Centrally located in Manhattan, this clinic serves a large variety of international travelers, including tourists, immigrants or their relatives, and business travelers, among others. Travelers' destinations are equally varied, reflecting the ethnic and cultural diversity of New York City.

Definitions

Diarrhea:

≥ 3 unformed stools in 24 hours, with or without associated symptoms such as fever, cramping, or abdominal pain

Travelers' diarrhea:

Diarrhea that begins while traveling (after arrival in a country) or within 10 days after return

Study period:

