Includes the 7 days prior to departure in which the pre-travel questionnaire and a biologic (stool) specimen is collected, the full duration of travel, and through 10 days maximum post-return from travel, or until both the post-travel questionnaire and submission of the post-travel biologic (stool) specimen is complete (a maximum of 17 days post-travel)

Travel companion (group):

Two or more study participants with a common relation (friends, colleagues, or relatives) with the same itinerary, who anticipate performing the same activities during travel

Trip duration:

The number of days spent in country; excludes air travel time

Severe TD:

Hospitalization to an inpatient ward either during travel or after travel with a diagnosis of diarrhea

Acquisition of AMR gene(s):

The presence in a post-travel biologic (stool) specimen of one or more antimicrobial resistance gene(s) that were not present in a pre-travel biologic (stool) specimen from the same person, and which is known to confer antimicrobial resistance to one or more antimicrobial agents ("resistome")

Medication compliance:

Full = participant takes all scheduled doses according to directions

Good = If <15% of BSS or placebo doses were missed during travel

Fair = If 15–30% of BSS or placebo doses were missed during travel

Poor = If >30% of doses were missed during travel

Questionnaire compliance:

Full = participant completes all questionnaires

Good = participant completes >80% of all during travel questionnaires, AND
both the pre- and post-travel questionnaires

Fair = participant completes between 30–80% of all during travel
questionnaires, including AT LEAST the pre-travel questionnaire

Poor = participant completes <40% of all during travel questionnaires, and AT
LEAST the pre-travel questionnaire

Biologic (stool) specimen compliance:

Full = BOTH specimens collected and sent

Fair = ONLY one specimen collected and sent

Poor = No specimens collected and sent

Loss to follow-up:

Failure to complete the post-travel questionnaire after three attempts to contact the participant or if submission of the post-travel biologic specimen (stool) occurs more than 10 days after return from travel or is not submitted

Participant Inclusion Criteria

Willing participants must meet the inclusion criteria as outlined here:

1. Be ≥ 18 and <70 years of age at the time of enrollment

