Participants will be asked to submit a web-based post-travel questionnaire within 10 days after return from travel, submit a biologic (stool) specimen, and provide all daily questionnaires that were completed during travel. This will be submitted via a pre-paid envelope addressed to the study clinic that was given to the participant when enrolled.

Study personnel will make follow-up telephone calls on days 3, 5, 7, and 10 after return as needed to encourage that the post-travel questionnaire, paper questionnaires from during-travel, and biologic (stool) specimens are all submitted.

The web-based post-travel questionnaire will include questions on:

1. The development of symptoms of TD since returning from abroad, including duration of symptoms
2. New antibiotic or other medication use
3. Adverse events

4. Contact with healthcare facilities or providers
5. Changes to travel itinerary during travel

Table 2. Schedule of CLINIC events (primary and secondary objectives):

	Stages			
	Pre-travel consultation (baseline)	Pre-travel (≤ 7 days before departure)	During travel	Post-travel (≤ 10 days after return)
Screening Questionnaire	X			
Informed Consent	X			
Pre-travel Questionnaire*		X		
Follow-up call(s)		X		X [†]
During travel Questionnaires			X	
Post-travel Questionnaire				X
Adverse Events Reporting			X	X

*Study personnel will call the participant to complete a pre-travel questionnaire 7 days before departure and to ensure that answers to the questions on the screening questionnaire have not changed. Reminder calls will occur as per **APPENDIX G**. If the traveler is leaving exactly 7 days after the pre-travel consultation/enrollment visit, this questionnaire can be performed at the pre-travel consultation/enrollment visit.

[†]Study personnel will call the participant within 3 days of return from travel to remind participants to complete their web-based post-travel questionnaire, submit any paper during travel questionnaires, and collect and submit the post-travel biologic (stool) sample. Reminder calls will occur as per **APPENDIX G**.

Laboratory Instruments

All participants will collect and submit a fresh biologic (stool) sample in the 7 days before departure and within 10 days after return. Participants will be

provided all instructions and materials necessary to collect and submit these samples at enrollment. All biologic (stool) specimens will be submitted by mail, and participants will be given pre-paid shipping materials.

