Dosing will begin on the flight prior to arrival in the destination and will cease once they return home. The study medications must be taken twice daily (a morning and an evening dose); with time zone changes, the first dose should be taken to ensure that no longer than 12 hours passes before a subsequent dose.

Before departure, participants will be provided, free of charge, all needed study medication for the duration of their trip. Participants will be encouraged to take all doses of their medication and appropriately document on their daily during travel questionnaires if a dose was missed or taken off schedule.

Outcomes

The outcomes of this study will include:

	Favorable Outcome	Non-favorable Outcome
Hypothesis 1: Prevention of TD	Prevention of TD in the intervention group	TD in the intervention group at a rate similar to placebo; intervention drug side effects; adverse events

Hypothesis 2: Acquisition of AMR genes	Reduced or no presence of travel-associated gut AMR genes in the intervention group	No reduction in the presence of travel-associated gut AMR genes in the intervention group
---	---	---

The participant's study period will end in the following circumstances:

1. The traveler meets criteria for removal (see Criteria for Removal from the Study)
2. The participant voluntarily withdraws from the study (see Procedures for Implementing and Documenting Informed Consent)
3. The participant completes all study activities and submits all study questionnaires and biologic (stool) specimens
4. The participant is lost to follow-up

The participants will be instructed at enrollment to stop the study medication for any of the following reasons (although they will still be instructed to answer their questionnaires and submit biologic [stool] specimens as scheduled):

1. Antibiotics or BSS (either provided by the study personnel for TD treatment, or taken as an over-the-counter remedy) are taken for TD or for another medical condition
2. Any severe adverse events as described, such as signs and symptoms of salicylism or neurotoxicity, occur
3. Hospitalization for any reason

Barring the reasons listed above, the study medication should be taken throughout the trip duration, even if diarrhea occurs, if possible.

Criteria for Removal from the Study

Participants will be removed from the study when any of the following criteria apply:

1. Do not complete the pre-travel questionnaire (see Definitions for compliance)
2. Loss to follow-up (see Definitions)

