The New York Center for Travel and Tropical Medicine clinic will be responsible for managing the questionnaire data in REDCap. The data will belong to The New York Center for Travel and Tropical Medicine, will be responsible, in collaboration with partners, for the reporting of findings. Data (questionnaires) done on paper will be stored confidentially at the clinic site and electronic data will be stored confidentially on the REDCap server (see Provision for Protecting Privacy/Confidentiality). The New York Center for Travel and Tropical Medicine clinic will have full access rights and CDC will have access to data (all de-identified) only with the approval of [name] and his team.

Coded laboratory data in a password-protected database, using the participant's unique ID, will be sent from the laboratory to the New York Center for Travel and Tropical Medicine for input into REDCap.

Quality Control and Assurance

Data quality will be controlled by input of data from screening questionnaires and paper copies of the during travel questionnaires into REDCap by one or two trained personnel at The New York Center for Travel and Tropical Medicine. We will place all data, exactly as received into the database. Data from the web-based questionnaires will be input directly into the REDCap database. Data will not be altered in any way.

Laboratory quality control will be performed by the study laboratorians to ensure that all specimens are tested with appropriate controls as necessary and applicable.

Every 3 months, data entered into REDCap will be checked for completeness and accuracy by the co-PIs (CDC would only access coded data) and/or study personnel; interim data analysis will be performed every 3 months as desired.

Bias in Data Collection, Measurement, and Analysis

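### A late or missing post-travel stool is enough on its own to remove a participant as lost to follow-up, although the TD endpoint needs no stool and no written analysis set keeps that participant in the TD comparison

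*Combined protocol and SAP*

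**What the plan says.** All references are to the combined protocol and SAP.

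- **Definitions, Loss to follow-up.** There are two limbs joined by *or*. One is an uncompleted post-travel questionnaire after three contact attempts. The other is that "submission of the post-travel biologic specimen (stool) occurs more than 10 days after return from travel or is not submitted".
- **Criteria for Removal from the Study.** "Participants will be removed from the study when any of the following criteria apply", and item 2 is "Loss to follow-up (see Definitions)". Under Outcomes, loss to follow-up also ends the participant's study period.
- **Definitions, Study period.** The period can run on past day 10 until both the post-travel questionnaire and the stool are in, to "a maximum of 17 days post-travel".
- **Definitions, Travelers' diarrhea.** The endpoint is "Diarrhea that begins while traveling (after arrival in a country) or within 10 days after return". Diarrhea is defined by stool count, so no specimen is involved.
- **Procedures.** "To address the secondary objective, participants will also be asked to provide pre- and post-travel biologic (stool) samples". The specimens are not tied to the primary objective.
- **Study Instruments, Post-travel.** "Participants will be asked to submit a web-based post-travel questionnaire within 10 days after return from travel".
- **Quality Control and Assurance.** "We will place all data, exactly as received into the database".
- **Sample Size and Power Calculation.** The 488 needed (244 per arm) are participants fully compliant with tablets and questionnaires. Stool is not mentioned. Planned enrolment is about 500.
- **Appendix I.** The TD shell (Table 2) has a total N column and names no analysis population. The AMR shell (Table 3) is separate.

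**The concern.** A rule built around a secondary-endpoint specimen decides whether someone stays in the study for the primary endpoint. A participant can complete every daily form and the post-travel form, have a known TD status, and still be removed because a specimen was posted late.

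With removal mandated and no analysis set written down, the analyst must decide whether removed participants count in the TD table. That decision could come after data have been seen, since the Study Timeline plans data analysis every three months. If the choice were exclusion, power would fall. The treatment estimate could also shift if stool non-return were related to both arm and TD.

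The definitions also conflict for one group. A stool submitted on days 11 to 17 after return falls within the study period, yet it makes the participant lost to follow-up.

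**Working it through.** **Inputs.** From Sample Size and Power Calculation: TD 40% on placebo and 0.40 × (1 − 0.30) = 28% on BSS, alpha 0.05 (taken as two-sided), power 80%, 244 per arm. From Estimated Number of Participants: about 500, so 250 per arm. The documents give no rate of late or missing stools, so every loss rate below is an assumption.

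**Step 1: reproduce the plan's figure.** Two proportions, pooled variance under the null, mean rate 0.34:

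n = [1.960 × √(2 × 0.34 × 0.66) + 0.842 × √(0.40 × 0.60 + 0.28 × 0.72)]² / 0.12²

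n = [1.313 + 0.559]² / 0.0144 = 243.4, so 244 per arm and 488 in total. This matches the plan.

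**Step 2: room for loss.** (500 − 488) / 500 = 2.4%, from all causes together.

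**Step 3: power if stool-only losses were dropped.** Power = Φ[(0.12 × √n − 1.313) / 0.6645]. This is the upper end of the cost: every stool non-returner has usable TD data, loss is random, and nothing else is lost.

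| Stool non-return (assumed) | Dropped of 500 | n per arm | Power | Cost vs 81.0% |
|---|---|---|---|---|
| 0% | 0 | 250 | 81.0% | none |
| 5% | 25 | 237.5 | 79.0% | 2.0 points |
| 10% | 50 | 225 | 76.8% | 4.2 points |
| 20% | 100 | 200 | 71.8% | 9.2 points |

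**Step 4: overlap with the questionnaire limb.** Appendix G puts both items on the same reminder calls, so non-return probably overlaps. Let s be stool non-return and q the share of those who also fail the questionnaire limb. Suppose questionnaire failures are lost in any case. The comparison is then n = 250(1 − qs) against n = 250(1 − s), and the stool limb alone removes 500s(1 − q).

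| Overlap q | Stool-only losses at s = 5 / 10 / 20% | Cost in power points |
|---|---|---|
| 0 | 25 / 50 / 100 | 2.0 / 4.2 / 9.2 |
| 0.50 | 12.5 / 25 / 50 | 1.0 / 2.2 / 5.0 |
| 0.75 | 6.25 / 12.5 / 25 | 0.5 / 1.1 / 2.6 |
| 1 | 0 | 0 |

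**Step 5: bias.** The planned crude odds ratio is (0.28/0.72) / (0.40/0.60) = 0.583. Dropping participants multiplies each arm-by-TD cell by its retention.

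- Loss of 20% in TD cases and 10% in others, the same in both arms: the factors cancel and the ratio stays 0.583. The same holds if loss is 20% in one arm and 10% in the other.
- Loss of 20% in one arm-by-TD cell and 10% elsewhere: 0.583 × 0.9/0.8 = 0.656 (placebo TD or BSS non-TD), or 0.583 × 0.8/0.9 = 0.519 (BSS TD or placebo non-TD).
- The same 20% in two opposite cells: 0.583 × (0.9/0.8)² = 0.738, or 0.583 × (0.8/0.9)² = 0.461.
- Relative protection behaves differently. With loss of 5% in TD cases and 20% in others, in both arms, placebo risk is 0.38/0.86 = 44.2% and BSS risk is 0.266/0.842 = 31.6%. Apparent protection is then 28.5% instead of 30%.

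**The case against.** **No exclusion is written.** A reader might infer that the plan drops stool non-returners from the TD analysis. It does not say so. Removal ends participation, and the stool limb can bite only after day 10, when the diaries are finished and the post-travel form is due. Little or no TD collection is cut short. Data are stored as received, the sample-size text counts tablet and questionnaire compliance only, and sending one specimen is graded as fair compliance. Table 5 costs stool testing for 250 participants, while Table 4 costs clinic events for 500. All of this suggests a TD denominator that does not depend on stool, and that part of the objection stands. But these are indications: storage is not an analysis rule, and nothing states the denominator.

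**Stool-only non-return may be uncommon.** Kits are prepaid, there are four reminder calls, the post-travel stool earns $50, and any payment requires good stool compliance (a grade the Definitions do not give for stool). This stands, and it pulls the likely cost towards the low end. The enrolment extension protects power only in part, because its trigger counts participants enrolled, not participants analysed.

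**The two time limits need not clash.** A stool by day 10 with a questionnaire by day 17 meets both definitions, so a general contradiction would be too strong a reading. The conflict is confined to stools submitted on days 11 to 17. It is real there, because both definitions speak of submission.

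**The questionnaire limb has the same weakness.** Someone with TD recorded abroad but no post-travel form is also classed as lost. This is correct, and the fix must cover it.

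**Conclusion.** The point holds as a defect in a stated rule. A secondary-endpoint specimen alone triggers removal from a trial whose primary endpoint is symptom-based, and no analysis set says what removal means for the TD comparison. It is worth correcting but does not undermine the trial.

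The harm is conditional on removed participants being dropped from the TD analysis. With no other losses, the power cost is at most 2.0 / 4.2 / 9.2 points at assumed stool non-return of 5% / 10% / 20%. It falls to zero with full overlap with questionnaire failure.

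Bias in the crude odds ratio needs loss that depends jointly on arm and TD. The values 0.656 and 0.519 are examples, and a reader should not take them as limits, since a two-cell pattern at the same rates gives 0.738 or 0.461. Relative protection can shift slightly when loss depends on TD alone. These figures are crude, whereas the Table 2 shell plans an adjusted odds ratio. Nothing in the documents shows that any of these loss patterns will occur.

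**What to change.** 1. Define loss to follow-up separately by objective: by questionnaire for TD and by post-travel stool for AMR. Treat a late or missing post-travel stool as missing for the AMR analysis only.
2. State that every randomised participant stays in the TD analysis by assigned arm with the TD data collected, subject to the consent terms for those who withdraw. This includes TD already recorded in the daily travel questionnaires when the post-travel form is missing.
3. Add a missing-data rule for participants with no TD recorded and incomplete questionnaire cover. The post-travel form can be filed before the 10-day TD window closes, so even some completed forms leave part of the window unobserved.
4. Reconcile the 10-day stool limit with the 17-day maximum. The investigators should choose the limit and give the reason. It is a trade-off for the AMR endpoint, since Current State of Knowledge notes that carriage may be short-lived.

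**Cost.** A change to one definition, a short analysis-set and missing-data statement, and an IRB amendment, which the Study Instruments section requires for such revisions. TD and AMR results will have different denominators, which the separate Table 2 and Table 3 shells already allow. No extra participants or visits are needed. Holding 488 by over-enrolment instead would take 488/0.95 = 514, 488/0.90 = 543 or 488/0.80 = 610 participants at the assumed loss rates.

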9. Have had diarrhea (see Definitions) anytime in the previous 30 days, have diarrhea at the pre-travel consultation, or develop diarrhea before departure
10. Have been given doxycycline for malaria prophylaxis for the current trip (due to possible drug-drug interactions and decreased absorption of the doxycycline) (27)
11. Have an allergy to any component of the placebo tablets

Estimated Number of Participants

We anticipate enrolling approximately 500 participants (see Sample Size and Power Calculation).

Sample Size and Power Calculation

A sample size of 488 participants with full compliance to medications and questionnaires (244 participants in each arm) is needed to fulfill the objectives [anticipated incidence of the endpoint as 40% incidence of TD with a 30% minimum intervention protection ($0.40-[0.4 \times 0.30] = 0.28$) with an alpha of 0.05, and 80% power].

Recruitment and Enrollment

All international travelers undergo a screening questionnaire at their pre-travel consultation to determine eligibility. This short questionnaire includes questions regarding the travelers' [see **APPENDIX A**]:

1. Age
2. Travel destination(s)
3. Trip duration
4. Acute and chronic medical conditions, including diarrhea
5. Contraindications to BSS administration
6. All current medications, including antibiotic use within the 30 days before screening
7. Willingness to participate in the trial and comply with the data collection requirements

This screening questionnaire will be administered to the traveler by study personnel at The New York Center for Travel and Tropical Medicine. The purpose will be to exclude those travelers who do not meet all inclusion criteria and those who meet any exclusion criteria (see Participant Inclusion / Exclusion Criteria). Travelers who meet the inclusion criteria and do not meet any exclusion criteria will be introduced to the project objectives and procedures, including the procedures for biologic (stool) specimen collection (see Laboratory instruments).

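### The 80% power is stated for 488 fully compliant participants, but 488 is later used as an enrolment count, no travelers' diarrhea analysis set is named, and a late or missing stool alone removes a participant

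*Combined protocol and SAP*

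**What the plan says.** **Who counts toward the sample size.** The Sample Size and Power Calculation section states: "A sample size of 488 participants with full compliance to medications and questionnaires (244 participants in each arm) is needed to fulfill the objectives". Its inputs are 40% TD, a minimum protection of 30% (hence 28% on bismuth subsalicylate, BSS), alpha 0.05 and 80% power. Under Definitions, full medication compliance is "Full = participant takes all scheduled doses according to directions" and full questionnaire compliance is "Full = participant completes all questionnaires".

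**How many are enrolled.** Estimated Number of Participants says "We anticipate enrolling approximately 500 participants". The section Response to New or Unexpected Findings and Changes in the Study Environment plans an interim analysis and a funding request if 488 have not been enrolled at two years, with the aim of continuing until power is adequate. There, 488 is a number enrolled.

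**Loss to follow-up and removal.** Under Definitions, loss to follow-up is either an uncompleted post-travel questionnaire after three contact attempts or, separately, "if submission of the post-travel biologic specimen (stool) occurs more than 10 days after return from travel or is not submitted". Criteria for Removal from the Study opens with "Participants will be removed from the study when any of the following criteria apply" and lists loss to follow-up second. The stool belongs to the secondary objective; the Procedures section says "To address the secondary objective, participants will also be asked to provide pre- and post-travel biologic (stool) samples for laboratory testing". The Study period definition, however, runs until "submission of the post-travel biologic (stool) specimen is complete (a maximum of 17 days post-travel".

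**What is compared.** Analytic tests says only that questionnaire data are compared between arms. The TD table shell in Appendix I has a total column with no population attached. Neither applies a compliance restriction.

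**The concern.** Three things do not fit together.

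- **Counting unit.** Power is stated for full compliers, while recruitment and the two-year check are counted in people enrolled. A trial with 488 enrolled passes that check however few of them can be analysed.
- **Removal rule.** A secondary-objective specimen can remove a participant whose primary-endpoint questionnaires are complete. The removal section does not say whether data already collected are analysed. The 10-day stool limit also conflicts with the 17-day study period.
- **Analysis set.** The power statement points to full compliers, whereas the analysis text and table shell point to everyone. A full-complier set would be selected on events after randomisation, some of them caused by TD: the Outcomes section directs participants to stop study medication when antibiotics or BSS are taken for TD. The documents do not say whether doses after such a stop count as missed. If they do, the set would exclude people partly because they had the outcome.

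At stake are the stated power and, more seriously, the validity of the primary comparison if the set is chosen after data are seen.

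**Working it through.** **Inputs from the plan.** p1 = 0.40; p2 = 0.40 × (1 − 0.30) = 0.28; alpha 0.05; power 80%; equal arms (block randomisation). Sidedness is not stated; a two-sided test reproduces the plan's figure.

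**Step 1: reproduce 244 per arm.** Pooled two-proportion formula without continuity correction, with p̄ = 0.34:

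n = [1.960 √(2p̄(1−p̄)) + 0.8416 √(p1(1−p1)+p2(1−p2))]² / (p1−p2)²

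= (1.960 × 0.6699 + 0.8416 × 0.6645)² / 0.12² = 243.4, so 244 per arm and 488 in all.

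Power(n) = Φ{[0.12√n − 1.960 × 0.6699] / 0.6645}; at n = 244 this is 80.1%. The plan's arithmetic is right.

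**Step 2: the margin.** 500 − 488 = 12, and 12/500 = 2.4%.

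**Step 3: power when TD status is missing in a share d.** The documents give no rate, so d is an assumption. Per-arm n is 250(1−d) at 500 enrolled and 244(1−d) at 488 enrolled, the number at which the two-year check is satisfied.

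| d (assumed) | 500 enrolled | 488 enrolled |
|---|---|---|
| 0% | 81.0% | 80.1% |
| 5% | 79.0% | 78.0% |
| 10% | 76.8% | 75.8% |
| 20% | 71.8% | 70.8% |

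**Step 4: non-adherence in an all-randomised analysis.** Step 3 keeps 28% in the BSS arm, which assumes that non-adherence costs no efficacy. As an illustration, if 10% of that arm had no benefit, p2 = 0.9 × 0.28 + 0.1 × 0.40 = 0.292. Power at 500 enrolled is then 72.0% with all observed and 67.4% with 10% unobserved.

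**Step 5: how far this depends on 30% protection.** Current State of Knowledge gives 41–65% protection at 2.1 g/day, the daily total stated for the active arm. At 41%, p2 = 0.40 × 0.59 = 0.236, and 500 enrolled gives 96.4% and 94.4% power at 10% and 20% unobserved. The 35% quoted in the same section refers to 1 g daily and is not the matching benchmark.

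**Step 6: the removal rule.** The two limbs of the loss-to-follow-up definition are joined by *or*. A participant with every daily and post-travel questionnaire complete, but no stool by day 10, meets the second limb and therefore the second removal criterion. A stool sent on days 11 to 17 falls inside the study period and outside the loss rule at once.

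**The case against.** **Removal may not mean exclusion.** No passage says that a removed participant's data are discarded. Quality Control and Assurance has all data entered as received, and stool-triggered removal arises after travel, when most TD data exist. This stands: a reader might infer that the plan throws away primary-endpoint data, but that is a risk left open by silence, not a stated rule.

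**The analysis may already be unrestricted.** The analysis text and table shell compare arms with no compliance filter. Also true, so it cannot be said that the plan prescribes a full-complier analysis. But no set is named, and the only section that describes who counts names full compliers.

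**Power may be ample.** At 41% protection it is, and compensation tied to compliance, follow-up calls on days 3, 5, 7 and 10 after return, and three-monthly completeness checks should limit losses. This confines the power shortfall to the 30% minimum that the plan itself chose. It does not settle the analysis set or the removal rule, which no effect size repairs.

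**More participants may be needed.** Keeping 488 countable would take 514, 543 or 610 enrolled at 5%, 10% or 20% loss (488 divided by 0.95, 0.90 or 0.80). A reader might conclude that enrolment must rise. The documents give no loss rate that would justify one of these numbers, and the budget is for 500. Restating power is enough.

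**The eligibility re-check.** The pre-travel telephone re-check follows randomised dispensing, but it is blinded and precedes the first dose. Excluding people found ineligible there need not bias the arms. Either choice is defensible if stated in advance.

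**Conclusion.** The point holds and should be fixed. The 488 is computed correctly but attached to a population that the rest of the plan neither recruits to nor names for analysis, and the two-year check does not measure it. At 500 enrolled and 40% vs 28%, the stated 80% survives only if about 12 or fewer lack TD status, and then only if non-adherence costs no efficacy. Under the assumed missing rates, power is 79.0% to 71.8%.

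The documents do not show that the trial is underpowered: the loss rates are assumptions, and the shortfall disappears at the protection they report for 2.1 g/day. The more durable defects are the unnamed TD analysis set and a removal rule that ties primary follow-up to a secondary specimen.

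**What to change.** 1. **Definitions and removal.** Split loss to follow-up: TD follow-up is lost only when TD status is not obtained; stool timing or absence affects only the resistance-gene analysis. Reconcile the 10-day and 17-day limits. State under Criteria for Removal that data collected before removal are kept and analysed.

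2. **Primary TD analysis.** Name the set: all randomised participants with TD status obtained, in their assigned arm, regardless of adherence, study-drug stop or stool submission. Define TD status obtained by one pre-specified questionnaire-completion rule, applied whatever outcome is reported, so that membership does not depend on the result. Add sensitivity analyses that (a) include TD reported below that threshold and (b) count departed participants without status first as TD, then as no TD. Full compliers are a sensitivity analysis only; say there whether doses after a directed stop count as missed. State in advance whether participants found ineligible at the pre-travel re-check are kept.

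3. **Power statement.** Give the power expected at about 500 enrolled: 81.0% with all observed, and 79.0%, 76.8% or 71.8% with 5%, 10% or 20% not (assumed). Note that these assume no efficacy loss from non-adherence, and give the 72.0% and 67.4% illustration.

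4. **Monitoring.** Have the three-monthly check report the number with TD status, pooled over arms. State that the 488 in the two-year check is an enrolment count and does not by itself show 80% power. Do not make the new count an automatic trigger for further enrolment.

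**Cost.** Protocol wording, a few extra analyses and a less favourable stated power. The check already exists, and no increase in enrolment is required.
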